**52472821.6.0000.5347 – Date:03/28/2022**

# STUDY PROTOCOL

## Study design and sample

This is a randomized clinical trial study to be carried out with healthy, strength-untrained women adult, with a strict vegetarian or non-vegetarian dietary pattern.

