## Inclusion criteria

- Age  $\geq 19$  and  $\leq 50$  years;
- Body mass index (BMI)  $< 30$  kg/m^2;
- Be a strict vegetarian or non-vegetarian for at least 6 months;
- Not performing regular physical exercise for at least 6 months.

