## Sample size calculation

The sample size was calculated generating 2 experimental groups: strict vegetarians (SV) and non-vegetarians (NV). 5% significance level and 95% statistical power will be considered. The result of the calculation (72 participants) was considered with a possible sample loss of 22.2%. Thus, 44 subjects will be needed in each group, totaling 88 participants. The sample size was calculated using the SAS Studio software (SAS Institute Inc., Cary, NC, USA).

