## **Logistics**

The recruitment of individuals for research will take place in a continuous flow, through dissemination through posters that will be fixed on the university premises, flyers that will be distributed at the Ecological Fair of Redenção (where there is a large circulation of vegetarians), vegetarian restaurants in region, as well as through social networks. Interested parties may contact the team via email, social media or in person. After the preliminary verification of the inclusion and exclusion criteria, a virtual meeting (phone or video call) will be held to provide information about Phases I (baseline) and II (16 weeks of strength training protocol participation) of the study and also to clarify doubts. Interested parties will be informed that participation in Phase I of the study is not conditioned to participation in Phase II, since, even if there is interest, only those who meet the specific eligibility criteria for such, referring to the evaluation of the average daily protein intake. Interested parties will receive a virtual copy of the Free and Informed Consent Term, which will clarify the research objectives and other relevant aspects, and will only participate in the research upon confirmation of agreement with the Term, which can be obtained by text, image or audio. Then, participants will be instructed to complete the 3-day food record and also to count the number of steps with the pedometer during 7 consecutive days. In the week following the end of data collection, participants will be invited to attend face-to-face assessments at the Exercise Research Laboratory at UFRGS.

At the first meeting, an anamnesis will be applied, body mass and height will be evaluated to determine the body mass index for a detailed review of the eligibility criteria. Then, the following evaluations will be performed: Body composition (Anthropometry, Dual Emission X-ray absorptiometry and ultrasonography), maximum and dynamic strength by isokinetic dynamometer (familiarization) and vertical jump power (familiarization). On the same day, the

International Physical Activity Questionnaire will be applied to also assess the participants' level of physical activity (CRAIG et al., 2003).

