A second face-to-face meeting will be scheduled with an interval of at least 48 hours after the first one to carry out the maximum and dynamic strength by isokinetic dynamometer and vertical jump power tests. Also, the knee extensors, knee flexors and plantar flexors, one maximum repetition test (1MR) familiarization will be realized. At third face-to-face meeting, the 1MR tests of knee extensors, knee flexors and plantar flexors will be evaluated. Body composition assessments of all participants and performance tests will be performed by physical educators. The 3-day food record and anamnesis will be performed and analysed by a nutricionista, equally trained for these tasks. Thus, the participants will started the 16 weeks of strength training protocol. After 1 week of the ending of strength training protocol the participants will repeat the measurements and tests realized at baseline in more three days to of face-to-face meeting. All face-to-face meetings with the participants to carry out the assessments will take place in the Neuromuscular Sector of the Exercise Research Laboratory, located at the School of Physical Education, Physiotherapy and Dance at UFRGS.

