### **Statistical analysis**

The results will be presented using descriptive statistics mean  $\pm$  standard deviation (SD) for variables with normal distribution and median (minimum – maximum) for non-parametric data. The normality of data distribution will be assessed using the Kolmogorov-smirnov test. In order to compare the neuromuscular characteristics, food intake and body composition of both groups, the T Test - independent, or the non-parametric alternative, Mann Withney's U

Test will be used. To assess whether the protein intake of strict vegetarians and non-vegetarians reaches the daily recommendation, the simple T-test or Wilcoxon's Test for Single Sample will be used, according to the data distribution. For correlations between neuromuscular parameters, food intake and body composition of strict vegetarians and non-vegetarians, the Pearson test ( $r$ ) will be used for continuous variables that presented normal distribution and the Spearman (Rho) test will be used when the variable does not present a normal distribution and/or or in ordinal variable. Correlation values (  $r$  or Rho ) will be classified as: "biologically negligible" (between 0.3 and -0.3); "weak" (between 0.31 and 0.5 or -0.31 and -0.5); "moderate" (between 0.51 and 0.7 or -0.51 and -0.7); "strong" (between 0.71 and 0.9 or -0.71 and -0.9); and "very strong" (when  $> 0.9$  or  $< -0.9$ ) (MUKAKA, 2012). The level of physical activity will be evaluated using the chi-square test of homogeneity of proportions. Calculations will be performed in SPSS software (version 25) and a significance level of 5% ( $p > 0.05$ ) will be adopted.

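### The study is labelled a randomized trial, but the comparison it is sized for is between diets the women already follow, so that comparison is not randomised and its unadjusted tests cannot separate diet from age or activity

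*Combined protocol and SAP*

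**What the plan says.** - **Design label.** The Study design and sample section announces "a randomized clinical trial study to be carried out with healthy, strength-untrained women adult, with a strict vegetarian or non-vegetarian dietary pattern".
- **How a woman comes to be in a group.** Under Inclusion criteria she must "Be a strict vegetarian or non-vegetarian for at least 6 months". The same list allows ages 19 to 50, requires BMI below 30 kg/m² and excludes recent regular exercise.
- **What is sized.** Under Sample size calculation: "The sample size was calculated generating 2 experimental groups: strict vegetarians (SV) and non-vegetarians (NV"). The total is 72, raised to 88 (44 per group) for losses.
- **What is compared.** Under Statistical analysis: "In order to compare the neuromuscular characteristics, food intake and body composition of both groups, the T Test - independent", with Mann-Whitney as the alternative. No covariate is named.
- **Activity data.** Under Logistics, women are asked to "count the number of steps with the pedometer during 7 consecutive days", and the "International Physical Activity Questionnaire will be applied to also assess the participants' level of physical activity". The Statistical analysis section uses activity level only in a chi-square test of homogeneity.
- **Entry to training and repeat measurement.** Also under Logistics, Phase II takes "only those who meet the specific eligibility criteria for such, referring to the evaluation of the average daily protein intake", and after training "the participants will repeat the measurements and tests realized at baseline". The Statistical analysis section does not say whether the between-group test uses baseline, post-training or change values.

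**The concern.** Random allocation is what would allow a group difference to be attributed to the group factor. A reader who meets the word randomized in the design sentence, and then sees the two diets called experimental groups, may carry that licence over to the diet contrast. It does not apply there.

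Without allocation, women who chose a strict vegetarian diet may also differ in age, habitual activity and other respects that affect strength and body composition. The plan measures age and activity but uses neither to adjust the comparison. A chi-square test of activity can reveal an imbalance; it does not correct the strength or body composition result for it. What is at stake is the meaning of the main result: a description of two groups of women, or an effect of diet.

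**Working it through.** **1. The label against the contrast.** This step needs no number.

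| Question | Answer in the plan | Section |
|---|---|---|
| What is the design called? | Randomized clinical trial | Study design and sample |
| Which groups are sized? | Strict vegetarian, non-vegetarian | Sample size calculation |
| Which groups are compared? | The same two; no others are named | Statistical analysis |
| When is membership fixed? | At least 6 months before entry | Inclusion criteria |

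A characteristic fixed before entry cannot be assigned by the study, so the sized contrast is not randomised.

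**2. The plan's own sample size.** 72 × (1 + 0.222) = 87.98, rounded up to 88, or 44 per group. This reproduces the stated total. The 72 itself cannot be reproduced, because no effect size, SD or endpoint is given. With 36 per group, 95% power and a two-sided 5% t test (sidedness is not stated, so this is assumed), the detectable difference is 0.862 SD.

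**3. How far an unadjusted test could mislead.** The imbalances are assumptions. Suppose diet has no effect, a covariate differs by g SD between groups, and it correlates r with the outcome. The groups then differ by r × g SD. With n = 36 per group the noncentrality is r × g × √(n/2) = r × g × 4.243, on 70 degrees of freedom (critical value 1.994).

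| g | r | r × g | Noncentrality | Unadjusted rejection | Adjusted rejection |
|---|---|---|---|---|---|
| 0.2 | 0.3 | 0.06 | 0.255 | 5.7% | 4.8% |
| 0.5 | 0.3 | 0.15 | 0.636 | 9.6% | 5.2% |
| 0.5 | 0.4 | 0.20 | 0.849 | 13.3% | 5.0% |

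The unadjusted column is exact. The adjusted column is simulated (20,000 trials per row; linear model with group, age and activity, both measured without error). If age and activity are both shifted and activity is measured with reliability 0.7, the unadjusted rates are 7.8%, 24.4% and 38.9%, and the adjusted rates 5.0%, 5.5% and 5.9%. A larger sample does not help: with 44 per group the 0.5 SD rows rise to 10.7% and 15.3% unadjusted.

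**4. Training response.** Assume a 0.5 SD baseline difference between diets, equal training gain, and pre-post correlation ρ. (Simulated, 20,000 trials per case, 36 per group.)

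| Baseline difference | Analysis | ρ = 0.7 | ρ = 0.8 | ρ = 0.9 |
|---|---|---|---|---|
| Stable | Baseline-adjusted | 13.6% | 10.5% | 7.7% |
| Stable | Change score | 5.0% | 5.0% | 5.2% |
| Transient | Baseline-adjusted | 4.9% | 4.8% | 5.3% |
| Transient | Change score | 12.7% | 9.8% | 7.7% |

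In both failing cases the bias is 0.5 × (1 − ρ) SD, for example 0.15 SD at ρ = 0.7. Stable means that the difference persists in full; transient means that it shrinks to ρ × 0.5 SD after training. At a 0.2 SD baseline difference all rates lie between 4.8% and 6.3%. Neither analysis is safe alone.

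**5. What adjustment costs.** Age plus pedometer steps takes the degrees of freedom from 70 to 68; age plus the questionnaire in three categories (assumed) takes them to 67. With balanced covariates the detectable difference stays at 0.862 SD. At a true difference of 0.861 SD, adding two covariates unrelated to the outcome changes simulated power from 95.0% to 94.5% if they are balanced, and from 94.7% to 91.4% if each differs by 0.5 SD between groups.

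**The case against.** The strongest reply is that the word randomized describes the study and not the diet contrast. The section lying between Logistics and Statistical analysis was not available for this review, and it may describe a factor that is randomised, for instance within the training programme. That stands: the study as a whole cannot be called non-randomised here, and the design sentence may need clarifying rather than reversing. It does not rescue the diet contrast, because nothing in that section could make a diet held before entry randomly assigned.

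Second, the plan is open about where the groups come from, and the text makes no causal claim about diet. Both are true. An unadjusted test is valid as description, and the harm arises only if the difference is read as a diet effect. The design label invites that reading.

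Third, the entry criteria limit confounding: women only, BMI below 30, no regular exercise, no chronic disease, and no protein supplements, caffeine or thermogenics. They narrow the room for bias without closing it, since age still spans 31 years (50 − 19) and habitual activity can differ among women who do not exercise regularly.

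Fourth, the error rates rest on assumed imbalances, and the mild case is close to 5%. That is right, and the required change does not depend on them.

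**Conclusion.** The concern holds. The comparison for which the study is sized is between pre-existing diets, so it is non-randomised. This follows from the text alone, with high confidence, and correcting the design sentence is essential.

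The consequences for the tests are less certain. On assumed imbalances in one covariate, the false rejection rate for a diet effect runs from 5.7% at 0.2 SD (correlation 0.3) to 13.3% at 0.5 SD (correlation 0.4). The documents do not allow the actual size or direction of bias to be known. Adjustment is therefore a recommendation, not a condition for validity of the descriptive comparison.

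**What to change.** **Required.** State in the design section that strict vegetarians and non-vegetarians form a non-randomised parallel-group comparison, and word diet conclusions as associations. If another factor is randomised, name it there and keep the word randomized for that factor only. The cost is one sentence and the wording of conclusions, with a less favourable design label. No participant, procedure or sample size changes.

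**Recommended.** Alongside the unadjusted test, report the diet comparison adjusted for age and one baseline activity measure chosen in advance (pedometer steps or the questionnaire). The data are already planned. The cost is two or three degrees of freedom and, in the least favourable case examined, a fall in power from about 95% to about 91%. Only measured confounders are handled.

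**Lesser details.** State the time point of each between-group test. For training response, compare change from baseline, with a baseline-adjusted model as a sensitivity analysis, and discuss any disagreement; the choice between them rests on an assumption that the data cannot test. Report by diet group how many women meet the Phase II protein-intake criterion.

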## Inclusion criteria

- Age  $\geq 19$  and  $\leq 50$  years;
- Body mass index (BMI)  $< 30$  kg/m^2;
- Be a strict vegetarian or non-vegetarian for at least 6 months;
- Not performing regular physical exercise for at least 6 months.

## Exclusion criteria

- Having chronic diseases, such as systemic arterial hypertension, diabetes mellitus, cardiomyopathy, etc.;
- Present physical limitations or musculoskeletal problems, which contraindicate the performance of strength exercises;
- Make use of protein or amino acid food supplement, caffeine or other thermogenic substances;

## Sample size calculation

The sample size was calculated generating 2 experimental groups: strict vegetarians (SV) and non-vegetarians (NV). 5% significance level and 95% statistical power will be considered. The result of the calculation (72 participants) was considered with a possible sample loss of 22.2%. Thus, 44 subjects will be needed in each group, totaling 88 participants. The sample size was calculated using the SAS Studio software (SAS Institute Inc., Cary, NC, USA).

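### The stated 22.2% loss is the margin added to the 72 required; the 88 enrolled can lose only 18.2% and still leave 72

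*Combined protocol and SAP*

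**What the plan says.** The Sample size calculation section of the combined protocol and SAP plans two groups, strict vegetarians and non-vegetarians. It sets the error rates as follows: "5% significance level and 95% statistical power will be considered". It then allows for loss: "The result of the calculation (72 participants) was considered with a possible sample loss of 22.2"%. The enrolment target follows directly: "Thus, 44 subjects will be needed in each group, totaling 88 participants".

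Neither this section nor any other says whether the 22.2% is a share of the 72 required or of the 88 enrolled. The Logistics section distinguishes a baseline phase from the 16-week training phase and notes that "participation in Phase I of the study is not conditioned to participation in Phase II". It does not say which phase the 88 counts.

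**The concern.** The percentage is presented as an expected loss, and participants can be lost only from those who enter the study. A reader would therefore take the sentence to mean that 22.2% of the 88 could drop out and the required 72 would still be there. The number 88 does not provide that much protection.

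What is at stake is the tolerated dropout. The trial has 16 weeks of training followed by three further assessment days, so attrition will be tracked and reported. This sentence is the plan's only benchmark for it. Anyone using 22.2% as the limit could believe the target of 72 had been met when it had been missed by a few women.

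**Working it through.** **Inputs**, all from the Sample size calculation section: 72 required in total (36 per group, with equal groups); loss allowance 22.2%; 88 enrolled (44 per group); 5% significance level; 95% power.

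**1. Reproduce the plan's 88.**

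- Mark-up on the required number, n × (1 + d): 72 × 1.222 = 87.98, so 88. Per group, 36 × 1.222 = 43.99, so 44. This matches.
- Division by the retained share, n / (1 − d): 72 / 0.778 = 92.5, so 93. Per group, 36 / 0.778 = 46.3, so 47, or 94 in total. This does not match.

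Only the mark-up gives 88.

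**2. Express the same margin on each base.** The margin is 88 − 72 = 16 women.

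- Share of those required: 16/72 = 8/36 = 22.2%.
- Share of those enrolled: 16/88 = 8/44 = 18.2%.

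Check: 72 / (1 − 16/88) = 88 exactly.

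**3. What remains if 22.2% of the enrolled women are lost.** 88 × 0.222 = 19.5 lost, and 88 × 0.778 = 68.5 remain (34.2 per group). In whole women per group:

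| Lost of 44 | Share lost | Left per group | Left in total |
|---|---|---|---|
| 8 | 18.2% | 36 | 72 |
| 9 | 20.5% | 35 | 70 |
| 10 | 22.7% | 34 | 68 |

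**4. Illustrative effect on power.** The section gives no outcome, effect size, SD, test or sidedness, so the 72 itself cannot be reproduced. The figures below assume a comparison of two means that has 95% power at the planned size, with alpha 0.05.

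- Normal approximation, with the standard error shrinking as the square root of n, at 68 instead of 72. Two-sided: Φ((1.960 + 1.645) × √(68/72) − 1.960) = 93.9%. One-sided: Φ((1.645 + 1.645) × √(68/72) − 1.645) = 94.0%.
- Two-sample t test (noncentral t), with the standardised effect d back-solved from 95% power and then evaluated at 34 per group. Two-sided: 93.8% (d = 0.8616, solved at 36 per group) to 94.4% (d = 0.8742, solved at 35 per group). One-sided: 93.9% (d = 0.7830) to 94.5% (d = 0.7944).

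**The case against.** The strongest reply is that nothing is miscalculated. The percentage is attached to the 72, it equals 16/72, and as a mark-up on 72 the printed numbers agree. Adding a percentage to the required number is a common, if rough, way to allow for dropout, and the documents do not define loss as a share of those enrolled. This stands as far as it goes: 88 is correctly computed on that base. It does not rescue the label. The allowance exists so that 72 women remain after losses, and a 22.2% loss among the 88 does not leave 72.

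A second reply is that a shortfall of four women is the high end. Losing 20 of 88 is 22.7%, slightly more than stated. The largest whole-number loss within 22.2% is 19 of 88 (21.6%), which leaves 69; counted within groups it is 9 of 44 (20.5%), which leaves 70. This is fair. The shortfall is 2 to 4 women depending on rounding, and it stays below 72 in every case.

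A third reply is that rewriting the figure as 18.2% presumes what the sponsor intended. If 22.2% of enrolled women really are expected to drop out, the matching enrolment is 93 (94 with equal groups). That is correct. Even so, a statement that 88 covers losses up to 18.2% is true whatever dropout is expected, and it would make such a shortfall visible.

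The unclear phase to which the 88 belongs does not affect the result: 16/88 applies to whichever women make up the 88.

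**Conclusion.** The concern holds as a minor error in a stated figure. The loss that 88 can absorb while leaving 72 is 18.2% of those enrolled, not 22.2%. A 22.2% loss from the 88 would leave 68 to 70 women, depending on rounding. At 68, power would be about 94% instead of 95%, on the assumption that 72 gives 95% power in a two-group comparison of means.

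The percentages 16/72 and 16/88 need no assumption beyond reading a loss as a share of those who enter. The power figures are illustrative, and the conclusion does not depend on them. The calculation of 88 is not challenged, nothing follows unless losses exceed 18.2%, and the trial's conclusions are not threatened.

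**What to change.** Keep 88 and replace the sentence on loss with: *The 72 participants required were increased to 88 to allow for a loss of up to 18.2% of those enrolled (16/88).*

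This costs one sentence, with no extra enrolment and no change to design or analysis. If the sponsor does expect 22.2% of enrolled women to be lost, the corrected sentence will show that 88 does not cover it. Covering it would take the 93 (94 with equal groups) derived above, which is a separate decision for the sponsor.

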## Ethical aspects

This study was designed in accordance with the Regulatory Guidelines and Norms for Research Involving Human Beings (Resolution CNS/MS 466/13) and was submitted to the Research Ethics Committee of the Federal University

of Rio Grande do Sul (CEP/UFRGS). No data collection was initiated before the approval of this committee. Likewise, the researchers undertake to maintain the anonymity and confidentiality of the participants' data, which will be identified by codes and handled only by the research team, being used only for scientific purposes and presented in a grouped manner. All participants will be asked to sign the Consent Form at the time they enter the study.

## **Logistics**

The recruitment of individuals for research will take place in a continuous flow, through dissemination through posters that will be fixed on the university premises, flyers that will be distributed at the Ecological Fair of Redenção (where there is a large circulation of vegetarians), vegetarian restaurants in region, as well as through social networks. Interested parties may contact the team via email, social media or in person. After the preliminary verification of the inclusion and exclusion criteria, a virtual meeting (phone or video call) will be held to provide information about Phases I (baseline) and II (16 weeks of strength training protocol participation) of the study and also to clarify doubts. Interested parties will be informed that participation in Phase I of the study is not conditioned to participation in Phase II, since, even if there is interest, only those who meet the specific eligibility criteria for such, referring to the evaluation of the average daily protein intake. Interested parties will receive a virtual copy of the Free and Informed Consent Term, which will clarify the research objectives and other relevant aspects, and will only participate in the research upon confirmation of agreement with the Term, which can be obtained by text, image or audio. Then, participants will be instructed to complete the 3-day food record and also to count the number of steps with the pedometer during 7 consecutive days. In the week following the end of data collection, participants will be invited to attend face-to-face assessments at the Exercise Research Laboratory at UFRGS.

At the first meeting, an anamnesis will be applied, body mass and height will be evaluated to determine the body mass index for a detailed review of the eligibility criteria. Then, the following evaluations will be performed: Body composition (Anthropometry, Dual Emission X-ray absorptiometry and ultrasonography), maximum and dynamic strength by isokinetic dynamometer (familiarization) and vertical jump power (familiarization). On the same day, the

International Physical Activity Questionnaire will be applied to also assess the participants' level of physical activity (CRAIG et al., 2003).

A second face-to-face meeting will be scheduled with an interval of at least 48 hours after the first one to carry out the maximum and dynamic strength by isokinetic dynamometer and vertical jump power tests. Also, the knee extensors, knee flexors and plantar flexors, one maximum repetition test (1MR) familiarization will be realized. At third face-to-face meeting, the 1MR tests of knee extensors, knee flexors and plantar flexors will be evaluated. Body composition assessments of all participants and performance tests will be performed by physical educators. The 3-day food record and anamnesis will be performed and analysed by a nutricionista, equally trained for these tasks. Thus, the participants will started the 16 weeks of strength training protocol. After 1 week of the ending of strength training protocol the participants will repeat the measurements and tests realized at baseline in more three days to of face-to-face meeting. All face-to-face meetings with the participants to carry out the assessments will take place in the Neuromuscular Sector of the Exercise Research Laboratory, located at the School of Physical Education, Physiotherapy and Dance at UFRGS.

